8.1 STUDY APPROVAL, PATIENT INFORMATION, AND INFORMED CONSENT

This trial will be initiated only after all required legal documentation has been reviewed and approved by the respective IRB / IEC and CA according to national and international regulations. The same applies for the implementation of changes introduced by amendments.

Prior to patient participation in the trial, written informed consent must be obtained from each patient (or the patient's legally accepted representative) according to ICH GCP and to the regulatory and legal requirements of the participating country. Each signature must be personally dated by each signatory and the informed consent and any additional patient-information form retained by the Investigator as part of the trial records. A signed copy of the informed consent and any additional patient information must be given to each patient or the patient's legally accepted representative.

For Japan: The Investigator must give a full explanation to trial patients including the items listed below in association with the use of the patient information form, which is prepared avoiding the use of technical terms and expressions. The patient is given sufficient time to consider participation in the trial. The Investigator obtains written consent of the patient's own free will with the informed consent form after confirming that the patient understands the contents. The Investigator must sign (or place a seal on) and date the informed consent form. If a trial collaborator has given a supplementary explanation, the trial collaborator also signs (or places a seal on) and dates the informed consent.

The following items need to be included:

1. That the clinical trial is aimed at testing.
2. Objectives of the trial.
3. The name, title, and address of the investigator to contact.
4. Trial procedures.
5. Anticipated benefits of the investigational products and anticipated disadvantages to the patient.
6. Matters concerning other therapeutic measures.
7. Duration of participation in the clinical trial.
8. That the patient may withdraw from the trial at any time.
9. That patient's refusal of or withdrawal from participation in the trial does not cause any disadvantage to him or her.
10. That the monitors, the auditors, and the institutional review board are given access to the relevant source documents on condition that confidentiality of the patient is fully secured.
11. That privacy of the patient is kept.
12. The office of the medical institution to contact in the event of trial-related injury.
13. That necessary treatment is available to the patient in the event of trial-related injury.
14. Matters concerning compensation in the event of any trial-related injury.
15. The type of the IRB which is used for the reviews and deliberations on the matters such as appropriateness of conducting the clinical trial, the matters to be reviewed and deliberated by each IRB, and other matters concerning the IRBs involved in the clinical trial.
16. Other necessary matters concerning the clinical trial.

The patient must be informed that his/her personal trial-related data will be used by BI in accordance with the local data protection law. The level of disclosure must also be explained to the patient.

The patient must be informed that his / her medical records may be examined by authorized monitors (CML/Clinical Research Associate (CRA)) or Clinical Quality Assurance auditors appointed by BI, by appropriate IRB / IEC members, and by inspectors from regulatory authorities.

8.2 DATA QUALITY ASSURANCE

A quality assurance audit/inspection of this trial may be conducted by the Sponsor or Sponsor's designees or by IRBs/IECs or by regulatory authorities. The quality assurance auditor will have access to all medical records, the Investigator's trial-related files and correspondence, and the informed consent documentation of this clinical trial.

In order to ensure accurate, consistent, complete and reliable data the following measures will be taken:

- Representatives from each site will have the opportunity to attend or review material from an Investigator Meeting at which trial processes will be discussed.

- Central laboratory measurements are used for all blood samples (for exception see [Section 5.2.3](#))
- Centralized adjudication and assessment ensures a consistent allocation of clinical endpoints
- Regular onsite monitoring
- Coding of concomitant medications is according to the WHO Drug Dictionary and coding of adverse events is according to the MedDRA dictionary.
- O9290989F/0/82 ;34-/6:3/, 24/8,:3/ 2./ P:9<12472./ 692993/ 6/,-31=/6 186/29K 18 2./ 2319< 6929 0989F/0/82 986 989<>,1, ;<98 @LOMQCA R.1-. 1, 9?91<9=€/ 18 2./ JLMS
- *Steps to maintain the blind (refer to [Section 4.1.5.1](#))*

8.3 RECORDS

Electronic Case Report Forms for individual patients will be provided by the Sponsor, via remote data capture. See [Section 4.1.5.2](#) for rules about emergency code breaks. For drug accountability, refer to [Section 4.1.8](#).

8.3.1 Source documents

Source documents provide evidence for the existence of the patient and substantiate the integrity of the data collected. Source documents are filed at the Investigator's site.

Data entered in the eCRFs that are transcribed from source documents must be consistent with the source documents or the discrepancies must be explained. The Investigator may need to request previous medical records or transfer records, depending on the trial; current medical records must be available. Medical records must demonstrate eligibility.

For eCRFs all data must be derived from source documents.

In addition the following copies will need to be provided to the Sponsor:

- Screening ECGs (including reports of cardiac monitoring) and ECGs with clinically relevant changes detected during the course of the study should be provided to the Sponsor's designee.
- For sites participating in the Imaging Substudy: Magnetic Resonance Image/CT reports and images for the index event of stroke, possible re-imaging done before randomization and any imaging related to recurrent stroke will be analyzed by the Sponsor's designee. In addition MRIs (or CTs, if MRIs are not available) performed

during clinical routine (and corresponding reports) will be collected. (see [Appendix 10.6](#)).

- For events requiring adjudication (as noted in [Section 3.1.1.4](#)), supporting documentation and imaging (as needed and available) must be provided.
- In the case of recurrent stroke or death detailed results of the required diagnostic imaging for the index stroke must also be provided as part of the adjudication package.

8.3.2 Direct access to source data and documents

The Investigator / institution will permit trial-related monitoring, audits, IRB / IEC review and regulatory inspection, providing direct access to all related source data / documents. Electronic Case Report Forms and all source documents, including progress notes and copies of laboratory and medical test results must be available at all times for review by the Sponsor's clinical trial monitor, auditor and inspection by health authorities (e.g. Food and Drug Administration (FDA)). The CRA / on site monitor and auditor may review all eCRFs, and written informed consents. The accuracy of the submitted data will be verified by reviewing the documents described in [Section 8.3.1](#).

8.3.3 Storage of records

This section is only relevant to sites located in Japan only.

Storage period of records

Trial sites:

The trial sites must retain the source documents and essential documents for a period defined by the Japanese GCP regulation and the Sponsor's SOP.

Sponsor:

The Sponsor must retain the essential documents according to the Sponsor's SOPs.

When it is no longer necessary for the trial site to retain the source documents and essential documents, the Sponsor must notify the head of trial site.

8.4 LISTEDNESS AND EXPEDITED REPORTING OF ADVERSE EVENTS

8.4.1 Listedness

To fulfill the regulatory requirements for expedited safety reporting, the Sponsor evaluates whether a particular adverse event is "listed", i.e. is a known side effect of the drug or not. Therefore a unique reference document for the evaluation of listedness needs to be provided.

For DE this is the current version of the IB. For ASA this is the SPC of the HEXAL ASA 100 mg tablet. The current versions of these reference documents are to be provided in the ISF. No AEs are classified as listed for matching placebo and study design.

8.4.2 Expedited reporting to health authorities and IECs/IRBs

Expedited reporting of SAEs, e.g. SUSARs, to health authorities and IECs/IRBs, will be done according to local regulatory requirements. Further details regarding this reporting procedure are provided in the ISF.

8.6 COMPLETION OF TRIAL

When the trial is completed, the Investigator should inform the head of the trial site of the completion in writing, and the head of the trial site should promptly inform the IRB and Sponsor of the completion in writing.

The ethics committee (EC)/CA in each participating European Union (EU) member state, and where applicable, the respective authority as defined per local regulations for each other country, needs to be notified about the end of the trial (LPO, unless specified differently in [Section 6.2.3](#) of the CTP) or early termination of the trial.

8.7 PROTOCOL VIOLATIONS

For Japan: The Investigator or sub-Investigator should record all CTP violations. The Investigator should provide and submit the Sponsor and the head of the trial site the records of violations infringing the Japanese GCP or violations to eliminate an immediate hazard to trial patients and for other medically inevitable reasons.

8.8 COMPENSATION AVAILABLE TO THE PATIENT IN THE EVENT OF TRIAL RELATED INJURY

For Japan: In the event of health injury associated with this trial, the Sponsor is responsible for compensation based on the contract signed by the trial site.

10. APPENDICES

- [APPENDIX 10.1](#) CHA₂DS₂-VASc Score
- [APPENDIX 10.2](#) STUDY DRUG START, THROMBOSIS PROPHYLAXIS AND TRANSITION TO NON-STUDY MEDICATION
- [APPENDIX 10.4](#) HANDLING OF OUTCOME EVENTS
(BLEEDS AND MORTALITY/MORBIDITY EVENTS)
- [APPENDIX 10.5](#) NATIONAL INSTITUTE OF HEALTH STROKE SCORE

10.1 CHA₂DS₂-VASc SCORE

The CHA₂DS₂-VASc score ([P11-03557](#)) is a refinement of CHADS₂ score (Congestive heart failure, Hypertension, Age > 75, Diabetes, prior Stroke/TIA), which is a stroke risk score originally validated for and applicable to patients with atrial fibrillation. The CHA₂DS₂-VASc score extends the CHADS₂ score by assigning additional weight to the risk factor age and by including additional stroke risk factors, specifically vascular disease and gender, as displayed below in Table 10.1.1. The maximum CHADS₂ score is 6, whilst the maximum CHA₂DS₂-VASc score is 9. The higher the CHA₂DS₂-VASc score, the higher is the expected risk of thromboembolism (including stroke and SE, see [Table 10.1.2](#))

Table 10.1.1 Components of the scoring system with the acronym CHA₂DS₂-VASc

CHA ₂ DS ₂ -VASc Acronym	Score
Congestive heart failure/LV dysfunction	1
Hypertension	1
Aged ≥75 years	2
Diabetes mellitus	1
Stroke/TIA/TE	2
Vascular disease (prior MI, PAD, or aortic plaque)	1
Aged 65-74 years	1
Sex category (i.e. female sex*)	1
Maximum score	9

LV = left ventricular; MI = myocardial infarction; PAD = peripheral artery disease;
 TE = thromboembolism; TIA = transient ischemic attack. Based on [R10-5332](#).

*Note that female gender only scores one point if the patient has at least one other risk factor, and does not score any points in isolation.

Table 10.1.2 Stroke risk stratification with the CHA₂DS₂-VASc score (according to R10-5332)

CHA ₂ DS ₂ -VASc Score	Thromboembolic Event Rate during one year (%; 95% CI) ¹
0	0 (0-0)
1	0.6 (0.0-3.4)
2	1.6 (0.3-4.7)
3	3.9 (1.7-7.6)
4	1.9 (0.5-4.9)
5	3.2 (0.7-9.0)
6	3.6 (0.4-12.3)
7	8.0 (1.0-26.0)
8	11.1 (0.3-48.3)
9	100 (2.5-100)

¹Based on initial validation cohort reported by Lip et al actual rates of stroke in contemporary cohorts may vary from these estimates ([R10-5332](#)).

10.2 STUDY DRUG START, THROMBOSIS PROPHYLAXIS AND TRANSITION TO NON-STUDY MEDICATION

10.2.1 When to start study drug following treatment with parenteral anticoagulants, Vitamin K antagonists, or antiplatelets

The following recommendations are provided for guidance only:

Parenteral anticoagulant pre-treatment (e.g. Heparins)

UFH or LMWH/injectable anticoagulant (if given) should be stopped prior to the first dose of study drug. Study drug should be initiated with the following suggested time windows:

- Continuous UFH/other continuous i.v. anticoagulants: initiate study drug at the time the UFH/ other continuous i.v. anticoagulant is stopped
- Bolus of UFH: initiate study drug 6 hours after the bolus injection of UFH
- Low-molecular Weight Heparin/other subcutaneous (s.c.) injectable anticoagulants: initiate study drug 0-2 hours prior to the time that the next dose of the LMWH/other s.c. injectable anticoagulant would be due.

Vitamin K antagonists (VKAs)

- The Vitamin K antagonist should be stopped. Study medication can be given as soon as the INR is < 2.0 .

Antiplatelet pre-treatment

(i.e. ASA, clopidogrel, ticlopidine, prasugrel, ticagrelor, dipyridamole, dipyridamole+ASA, at any labeled maintenance dosage)

- Non-study antiplatelets should be stopped prior to the first dose of study drug. Study drug can be initiated *at any time-point* after discontinuation of the non-study antiplatelet, with one exception: After a loading dose of ticagrelor, clopidogrel or prasugrel has been taken, a minimum of 2 hours should elapse before the first dose of study medication can be given.

Please note that ASA (commercial drug/over the counter medication) ticagrelor, clopidogrel, dipyridamole, dipyridamole+ASA and prasugrel are restricted medications and may not be taken during treatment with study drug. (Note: optional concomitant ASA assigned by IRT may be given, see [Section 4.1.1](#)).

10.2.2 Thrombosis prophylaxis or temporary requirement for parenteral anticoagulant or antiplatelet(s)

Immobilization or intervention may require temporary thrombosis prophylaxis with e.g. UFH or LMWH or antiplatelet(s). Certain interventions may require the use of parenteral anticoagulants.

The following rules should apply, if thrombosis prophylaxis/parenteral anticoagulants are considered temporarily necessary by the Investigator:

[figure not shown]
- Temporarily stop study medication. It is recommended to wait 12 hours after the last dose of study medication before switching to a parenteral anticoagulant (e.g. UFH, LMWH). Antiplatelet(s) can be started at any time after last dose of study drug.

The period of thrombosis prophylaxis should be kept to a minimum. For recommendations how to switch back to study drug (DE or ASA) see [Section 10.2.1](#).

10.2.3 Transition to non-study antithrombotic treatment with early study drug discontinuation or at the end of the trial

Patients actively taking study drug at their final treatment visit and patients who stop study medication early may need to switch to a non-study antithrombotic treatment at the Investigator's discretion. The following recommendations are provided for guidance only

- If the non-study treatment will be antiplatelet agent(s), this medication can be initiated at any time-point after last intake of study medication.
- If the non-study treatment will be DE or another NOAC (such as rivaroxaban, apixaban or edoxaban), the first dose of DE (or other NOAC) should be taken at the time that the next dose of study medication would have been due.
- If the non-study treatment is a Vitamin K antagonist, the starting time of the VKA should be adjusted according to the patient's CrCl as follows:
 - CrCl \geq 50 mL/min: start VKA 3 days before discontinuing study drug
 - CrCl \geq 30- < 50 mL/min: start VKA 2 days before discontinuing study drug

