In Phase I drug-drug interaction studies there was no significant influence of DE on the PK of atorvastatin, diclofenac or digoxin (P-glycoprotein (P-gp) substrate), and the exposure of dabigatran was not significantly altered by these drugs. Dabigatran etexilate and dabigatran are not metabolized by the cytochrome P450 system and have no in vitro effects on human cytochrome P450 enzymes. There was, however, an effect on DE bioavailability after co-administration with some P-gp inhibitors or inducers. The maximum increase, approximately 2.5 fold, in dabigatran exposure was observed after ketoconazole single and multiple dose co-administration while chronic rifampicin reduced the dabigatran exposure to 1/3 of control values. However, co-administration of P-gp inhibitors (such as amiodarone, quinidine and verapamil) in the long-term Phase III study, Randomized Evaluation of Long-Term Anticoagulant Therapy with Dabigatran Etexilate (RE-LY) (1160.26) had much smaller effects (increase of dabigatran plasma concentration of up to 16%) ([U09-3249-02](#)) than those observed in Phase I studies.

The PK and PD of dabigatran in subjects with normal renal function in comparison to patients with varying degrees of renal impairment (mild, moderate, severe and dialysis dependent end stage renal disease) have been studied in an open, group-comparison design trial of 36 subjects. In otherwise healthy volunteers with mild ($\text{CrCl} \geq 50$ and < 80 mL/min), moderate ($\text{CrCl} \geq 30$ and < 50 mL/min), and severe ($\text{CrCl} < 30$ mL/min) renal impairment, the area under the curves (AUCs) of dabigatran were increased 1.8, 2.7 and 6.8 fold respectively, compared to healthy volunteers with normal renal function ($\text{CrCl} > 80$ mL/min) ([U06-1704](#)). This is in accordance with the fact that dabigatran is mainly renally excreted.

The RE-LY trial was a Phase III, prospective, randomized, open-label, multinational trial of stroke prevention in patients with non-valvular AF at risk of stroke. A total of 18,113 patients were randomized to one of two blinded doses of DE (110 mg b.i.d. or 150 mg b.i.d.) or to warfarin (target INR 2.0-3.0) ([U09-3249-02](#)).

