- Patients who are found to have a CrCl <30mL/min during the course of the trial should have study drug temporarily discontinued (see [Section 5.2.3](#) for calculation of CrCl and risks of taking DE with reduced renal function). Labs can be repeated before stopping study drug if Investigator wishes to confirm initial lab result. The patient will be permanently discontinued from study drug, unless CrCl recovers to ≥ 30 mL/min within seven days. A patient should also be permanently discontinued from study drug if CrCl drops <30mL/min on two different occasions during the trial. During period of interruption, a patient can be treated per standard of care according Investigator's discretion. Guidelines for transitioning to non-study antithrombotic medications are provided in [Section 10.2.2](#).
- Patient noncompliance with study drug administration (per [Section 4.3](#))
- If a patient becomes pregnant or a pregnancy is suspected during the trial the investigational drug will be stopped, the patient will be discontinued from treatment and the patient will be followed up through the end of the trial and until birth or otherwise termination of the pregnancy. For further information, including the process for follow-up on the outcome of the pregnancy please see [Section 5.2.2.3](#).
- Withdrawal of consent

At the discretion of the Investigator/patient, an individual patient may be discontinued from study drug if:

- The patient is no longer able to continue study drug for other medical reasons (e.g., surgery, AEs, other diseases or concomitant therapies)
- In the opinion of the Investigator, continuation on the study drug is not in the patient's best interest, if eligibility criteria are being violated, or if the patient fails to comply with the protocol (e.g. non-attendance at trial assessments, and reason to be recorded in the electronic Case Report Form (eCRF)) or if the patient develops a high propensity for falls where Investigator deems a patient's potential risk for bleeding exceeds the potential benefits of study drug.
- The patients elects to stop taking study drug

The date of last dose of study drug and reason for study drug discontinuation will be recorded on the eCRF.

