For hemorrhagic stroke or other intracranial bleeding, consultation with a coagulation expert and a neurosurgeon is recommended. See “Major Bleeds” earlier in this section for details relating to how to manage bleeding.

In case of recurrent stroke during the trial, it is at the Investigator's discretion whether study medication will be restarted or whether the patients will be switched to appropriate standard of care antithrombotic treatment.

Reintroduction of study treatment following a stroke (i.e. after recurrent stroke)

The decision about when to restart study medication following a recurrent stroke is at the discretion of the Investigator (with the exception of strokes with mRS of 4 or higher, where restart is not allowed, unless the patient improves to a mRS of 3). [Table 4.1.4: 1](#) shows recommendations ([P12-02400](#)) on the earliest possible time point to start study medication. These recommendations in [Table 4.1.4: 1](#) also apply to restarting study medication after recurrent stroke. Cerebral hemorrhage must be excluded before study drug is restarted. If restarting study medication within 10 days of stroke in patients with mRS of 1, 2 or 3, re-imaging is required to rule out bleeding into the brain (for details see footnote of [Table 4.1.4: 1](#)).

Acute Coronary Syndrome (ACS)

In patients with documented or suspected ACS, study drug should be temporarily discontinued.

Medication Management of ACS

ASA, clopidogrel and glycoprotein IIb/IIIa inhibitors may be administered according to usual clinical practice. However, the concomitant use of these treatments with study medication may increase the risk of bleeding.

For the use of heparins (UFH or LMWH) or other anticoagulants to manage ACS, the following guidance is provided for consideration:

Unfractionated or low-molecular-weight heparin should be withheld until the aPTT is less than 1.5 x ULN (upper limit of normal):

- If the aPTT is between 1.2 and 1.5 x ULN, UF heparin may be commenced preferably without an intravenous loading dose and LMWH may be commenced at the usual therapeutic dose
- If the aPTT is above 1.5 times the ULN, it should be repeated every four hours until it falls below this level, after which heparin or other anticoagulation can be commenced.

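### Patients stopped because CrCl fell below 30 mL/min are referred to a section whose single 12-hour wait before a parenteral anticoagulant does not vary with renal function

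*Protocol*

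**What the plan says.** Four parts of the protocol bear on this.

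- **Section 3.3.4.1** sets the stop: "Patients who are found to have a CrCl <30mL/min during the course of the trial should have study drug temporarily discontinued". The stop becomes permanent unless CrCl is back to 30 mL/min or more within seven days, or if it falls below 30 on two occasions. For the gap in treatment it says: "During period of interruption, a patient can be treated per standard of care according Investigator's discretion". It then adds: "Guidelines for transitioning to non-study antithrombotic medications are provided in" Section 10.2.2. The description of Amendment 1 shows that this reference was added on purpose, for patients whose study drug is stopped because of reduced renal function.
- **Section 10.2.2** introduces its content as rules that should apply. It tells the investigator to interrupt study drug, and then: "It is recommended to wait 12 hours after the last dose of study medication before switching to a parenteral anticoagulant (e.g. UFH, LMWH". Antiplatelets may start at any time. No CrCl band appears in the text.
- **Table 4.2.1: 1** gives dabigatran half-lives by renal function and lengthens the stop before surgery as CrCl falls. The stop is 24 h (standard risk) or 2 days (high risk) at CrCl above 80, and 2 to 5 days or more than 5 days at CrCl below 30.
- **Section 10.2.3** says that the first dose of another NOAC "should be taken at the time that the next dose of study medication would have been due", whatever the CrCl. It has vitamin K antagonist (VKA) schedules for CrCl of 50 or more and for 30 to below 50. It has no text for CrCl below 30 and no rule for parenteral anticoagulants.

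**The concern.** The variable that triggers the stop is the one that governs how long dabigatran persists, yet the section to which these patients are sent ignores it. Elsewhere the protocol does scale by renal function: the pre-surgery table does so, and so do the VKA schedules next to the 12-hour text. Section 5.2.3 also warns that patients with decreased renal function may eliminate dabigatran slowly and are at increased risk of bleeding.

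What is at stake is patient safety. An investigator who follows the cross-reference for a patient on dabigatran may add heparin to a large residual level of the drug, in a group that the protocol itself regards as prone to bleeding.

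**Working it through.** The documents state no residual fraction, so there is no figure of the plan's own to reproduce. The check combines two stated inputs.

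**Inputs**
- Wait before a parenteral anticoagulant: t = 12 h (Section 10.2.2).
- Dabigatran half-life h (Table 4.2.1: 1): about 13 h at CrCl above 80; about 15 h at 50 to 80; about 18 h (18 to 24) at 30 to below 50; about 27 h (above 24) at CrCl below 30.
- Time to peak: 2 to 3 h after a dose, stated for normal renal function (Section 4.2.1). Used only as a sensitivity check.

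**Formula.** First-order elimination: fraction remaining = 0.5^(t / h).

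| CrCl (mL/min) | h | 12 / h | Remaining at 12 h |
|---|---|---|---|
| above 80 | 13 h | 0.92 | 52.7% |
| 50 to 80 | 15 h | 0.80 | 57.4% |
| 30 to below 50 | 18 h | 0.67 | 63.0% |
| below 30, lower bound | 24 h | 0.50 | 70.7% |
| below 30, central value | 27 h | 0.44 | 73.5% |

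For CrCl below 30 the wait is 0.44 of a half-life. Because the table gives the half-life as above 24 h, the wait is less than half a half-life and more than 70.7% remains on any value the table allows.

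**Sensitivity.** If decay is counted from a peak 2 to 3 h after the dose, 10 or 9 h have elapsed. With h = 27 the fraction of peak remaining is 0.5^(10/27) = 77% or 0.5^(9/27) = 79%. With h = 24 it is 75% or 77%. The range across these readings is about 71% to 79%.

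**Scale.** With h = 27, the table's own pre-surgery stops for CrCl below 30 leave 0.5^(48/27) = 29% at 2 days and 0.5^(120/27) = 4.6% at 5 days. Those stops serve a different purpose, so they show only that the protocol treats slow elimination as important in this band.

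**Does another section supply the missing instruction?**
- Section 10.2.3 has no parenteral rule and nothing for CrCl below 30, so reading the cross-reference as meant for 10.2.3 would not help.
- Section 4.2.1 says that reduced renal function must be taken into account, but does so in its surgical guidance and gives no interval.
- A coagulation-test condition for heparin appears in the acute coronary syndrome guidance. Outside emergencies, Sections 4.1.5.2 and 4.2.1 steer investigators away from such tests to protect the blind. For a non-emergency renal stop, the time rule is therefore the main working safeguard.

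**The case against.** The case on the other side has weight.

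- **It is guidance.** The 12 hours is recommended, and treatment during the interruption is left to the investigator, who may choose an antiplatelet. That stands, and it limits the claim to what can happen.
- **No stated threshold is breached.** The documents set no residual level above which heparin may not start, and about 53% remains at 12 h even at CrCl above 80. That also stands. The defect is that the wait does not vary with CrCl. For the same reason, a reader who wants to turn the half-lives into an equivalent waiting time would be using a benchmark that the documents do not contain.
- **Table 4.2.1: 1 answers a surgical question.** This is true of its stop times. Its half-lives are properties of the drug and apply in any setting.
- **The missing VKA row has a partial explanation.** The VKA schedules start the new drug before study drug ends, which does not fit patients whose study drug must already be stopped. That stands, but it leaves the NOAC and parenteral cases untouched.
- **The group may be small.** CrCl below 30, or an expected fall below it, is excluded at entry. No count is given.
- **A figure in 10.2.2 is not reproduced in the text available for review.** The finding is therefore limited to the visible text.

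Four stronger readings are tempting and not supported:
- *A direct conflict with the acute coronary syndrome guidance*, which says "Unfractionated or low-molecular-weight heparin should be withheld until the aPTT is less than 1.5 x ULN". That text is offered for consideration in a different clinical setting.
- *A predicted aPTT at 12 h in these patients.* The roughly 1.5-fold trough value in Section 4.2.1 is a median across RE-LY patients on 150 mg, not a group with CrCl above 80, so the ratio of half-lives cannot be applied to it.
- *Multiplying the residual by the rise in exposure.* Section 1.2 reports that AUCs "were increased 1.8, 2.7 and 6.8 fold respectively" in mild, moderate and severe impairment. Those were otherwise healthy volunteers in a 36-subject study, and trial patients already at CrCl 30 to below 50 are assigned the lower dose.
- *Bias in the bleeding analysis.* Counting bleeds up to 6 days after the last dose is the intended residual-effect rule and applies to both arms.

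**Conclusion.** The point holds as an internal inconsistency that bears on patient safety and should be corrected. The protocol refers patients stopped for CrCl below 30 mL/min to a single 12-hour wait, which by its own half-lives is about 0.44 of a half-life for them. About 73% of the drug then remains (about 71% at the 24 h bound), against about 53% at CrCl above 80.

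The conclusion assumes single-exponential elimination and the half-lives of Table 4.2.1: 1, and it concerns the dabigatran arm only. Under blinding the text applies to all patients, but only that arm carries residual dabigatran. How many patients would be affected, and how many of those would be given a parenteral anticoagulant, cannot be estimated from the documents. The point does not touch the sample size, the type I error or the primary efficacy analysis.

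**What to change.** Reconcile Section 3.3.4.1, Table 4.2.1: 1 and Appendix 10.2 (10.2.2 and 10.2.3). Either the section to which patients with CrCl below 30 mL/min are referred should contain an instruction for them that is consistent with the protocol's own half-lives, or the cross-reference in 3.3.4.1 should point to a place that does. The instruction should say what applies to a parenteral anticoagulant and to another NOAC, and should state whether the VKA schedules are meant to apply at all after a mandatory stop. It must also respect the limits on coagulation testing in Sections 4.1.5.2 and 4.2.1. The content of the clinical rule is for the sponsor to decide, and none is proposed here.

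The cost is a change of appendix wording and a letter to sites.
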